7.11.2 Clinical Laboratory Evaluations

7.11.2.1 Hematology and Serum Chemistry

Analysis Set:

Safety analysis set

Analysis variable(s):

Hematology

Red blood cell count, White blood cell count with differential (neutrophils, basophils, eosinophils, lymphocytes, monocytes), Hemoglobin, Hematocrit, Platelets

Serum Chemistry

ALT, Albumin, ALP, AST, Total bilirubin, BUN, Calcium, Chloride, Creatinine, Creatinine kinase, Cystatin C, eGFR, GGT, Glucose, Total cholesterol, Triglycerides, Phosphate, Potassium, Sodium, Total Protein, LDH

Categories:

Results of determination based on normal reference range [Below lower limit of normal range, Within normal range, Over upper limit of normal range]

Visit:

Weeks 0, 2, 4, 8, 12, 16 (postdose), 24, 40, and 52

Analytical method(s):

The following analysis will be performed for the above analysis variables by weight group ($< 50 \text{ kg}, \ge 50 \text{ kg}$) and in the combined weight groups.

When performing analyses on MAV, if a laboratory parameter has both lower and upper MAV criteria, an analysis will be performed for each. See "9.0 APPENDIX" for test items to be analyzed and definitions of MAV criteria.

The measurement at Week 16 will be performed after the study drug administration, while the measurement at other visits than Week 16 will be performed before the study drug administration.

- (1) Summary statistics for observed values and changes (each visit after administration [Week 2 to Week 52] Week 0) will be provided for each visit.
- (2) Case Plots
- (3) Shift tables showing results of determination based on normal reference range at Week 0 and each visit after administration
- (4) Overall frequency distributions of MAV during the Treatment Period

7.11.2.2 Urinalysis

Analysis set:

Safety analysis set

Analysis variable(s):

Quantitative variable(s)

Specific gravity, Protein, Creatinine, Albumin, Protein/creatinine ratio, Albumin/creatinine ratio

Qualitative variable(s)

Glucose, pH, Protein, Occult blood, Ketones

Categories:

Results of determination based on normal reference range [Below lower limit of normal range, Within normal range, Over upper limit of normal range]

Visit:

Weeks 0, 2, 4, 8, 12, 16 (postdose), 24, 40, and 52

Analytical method(s):

The following analyses (1), (2), and (4) will be performed for the quantitative variables by weight group ($< 50 \text{ kg}, \ge 50 \text{ kg}$) and in the combined weight groups.

The following analyses (3) and (4) will be per formed for the qualitative variables, by weight group ($< 50 \text{ kg}, \ge 50 \text{ kg}$) and in the combined weight groups.

The measurement at Week 16 will be performed after the study drug administration, while the measurement at other visits than Week 16 will be performed before the study drug administration.

- (1) Summary statistics for observed values and changes (each visit after administration [Week 2 to Week 52] Week 0) will be provided for each visit.
- (2) Case Plots
- (3) Shift tables at Week 0 and each visit after administration
- (4) Shift tables showing results of determination based on normal reference range at Week 0 and each visit after administration (variables with normal reference range)

7.11.3 Vital Signs and Weight

Analysis set:

Safety analysis set

Analysis variable(s):

Office sitting pulse rate

Office standing systolic blood pressure, Office standing diastolic blood pressure, Office standing pulse rate

Home sitting systolic and diastolic blood pressures

Height, Weight

Visit

Office sitting pulse rate: Weeks 0, 2, 4, 8, 12, 16 (postdose), 20, 24, 32, 40, 52, 54 (Follow-up Period)

Office standing blood pressure and pulse rate: Weeks 0, 12, 24, and 52

Home blood pressure: Week 0 (predose), Week 0 (postdose), Weeks 2, 4, 8, and 12

Height and weight: Weeks 0, 12, 24, 40, and 52

Analytical method(s):

The following analysis will be performed for the above analysis variables by weight group (\leq 50 kg, \geq 50 kg) and in the combined weight groups.

The measurement of office sitting pulse rate at Week 16 will be performed after the study drug administration, while the measurement at other visits than Week 16 will be performed before the study drug administration.

(1) Summary statistics for observed values and changes (each visit after administration [each visit other than Week 0] – Week 0) will be provided for each visit.

Home blood pressure will be provided for changes (each visit after administration [each visit other than Week 0 (predose)] – Week 0 [predose]).

- (2) Case Plots
- (3) Overall frequency distributions of home blood pressure during the Treatment Period. See "9.0 APPENDIX" for the criteria."

7.11.4 **12-Lead ECGs**

Analysis set:

Safety analysis set

Analysis variable(s):

Heart rate

RR interval

PR interval

QT interval

QTcF interval

QRS interval

Resting 12-lead ECG interpretation [Within normal limits, Abnormal but not clinically significant, Abnormal and clinically significant]

Visit:

Weeks 0, 12, 24, and 52

Analytical method(s):

The following analyses (1) and (2) will be performed for the above analysis variables excluding resting 12-lead ECG interpretation by weight group ($< 50 \text{ kg}, \ge 50 \text{ kg}$) and in the combined weight groups.

The following analysis (3) will be performed for resting 12-lead ECG interpretation by weight group ($< 50 \text{ kg}, \ge 50 \text{ kg}$) and in the combined weight groups.

- (1) Summary statistics for observed values and changes (each visit after administration [Week 12 to Week 52] Week 0) will be provided for each visit.
- (2) Case Plots
- (3) Shift tables at Week 0 and each visit after administration

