5.2 Endpoints

5.2.1 Primary Endpoints

Safety:

AEs, anthropometric (weight, height, and body mass index [BMI]) measurements, laboratory tests, resting 12-lead electrocardiogram (ECG), and vital signs (office standing blood pressure, office sitting pulse rate, office standing pulse rate, and home sitting blood pressure)

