13.1.5 Safety Analysis

[Primary endpoints]

AEs, anthropometric (weight, height and BMI) measurements, laboratory tests, resting 12-lead ECG, and vital signs (office standing blood pressure, office sitting pulse rate, office standing pulse rate, and home sitting blood pressure)

[Analytical methods]

The following analyses will be conducted with the safety analysis set.

1) AEs (Treatment-emergent AEs)

A treatment-emergent AE (TEAE) is defined as any AE occurring after the start of TAK-536 administration of the Treatment Period.

The incidence of TEAEs listed below will be analyzed. TEAEs will be coded using the Medical Dictionary for Regulatory Activities (MedDRA). The frequency distribution will be provided using the system organ class (SOC) and preferred term (PT) using MedDRA as follows:

- TEAEs
 - Drug-related TEAEs
 - Severity of TEAEs
 - Severity of drug-related TEAEs
 - TEAEs leading to study drug discontinuation
 - Serious TEAEs
 - TEAEs over time
- 2) Anthropometric (weight, height and BMI) measurements, laboratory tests, resting 12-lead ECG, and vital signs (office standing blood pressure, office sitting pulse rate, office standing pulse rate, and home sitting blood pressure)

For continuous variables, the observed values and the changes from the end of the Run-in Period (Week 0) will be summarized for each time point. In addition, individual figures of the observed values will be provided.

For categorical values, shift tables of the data before and after administration will be provided.

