5.0 ANALYSIS ENDPOINTS

Primary Efficacy Endpoint

<Safety>

AEs, anthropometric (weight, height, and body mass index [BMI]) measurements, laboratory tests, resting 12-lead electrocardiogram (ECG), and vital signs (office standing blood pressure, office sitting pulse rate, office standing pulse rate, and home sitting blood pressure)

Secondary Efficacy Endpoints

<Efficacy>

Office trough* sitting diastolic and systolic blood pressures

* Trough: The time point immediately before the next dosing, when the blood drug concentration is assumed to be lowest

Proportion of subjects who achieve the target blood pressure**

** Target blood pressure: < 95th percentile shown in Table 5.a Reference Blood Pressure Values of Children by Gender and Age for essential hypertension, < 90th percentile shown in Table 5.a Reference Blood Pressure Values of Children by Gender and Age for secondary hypertension

Table 5.a Reference Blood Pressure Values of Children by Gender and Age

					•	O
		Boy			Girl	
	90th	95th	99th	90th	95th	99th
6 years old	110/70	114/74	121/82	108/70	111/74	119/81
7 years old	111/72	115/76	122/84	109/71	113/75	120/82
8 years old	112/73	116/78	123/86	111/72	115/76	122/83
9 years old	114/75	118/79	125/87	113/73	117/77	124/84
10 years old	115/75	119/80	127/88	115/74	119/78	126/86
11 years old	117/76	121/80	129/88	117/75	121/79	128/87
12 years old	120/76	123/81	131/89	119/76	123/80	130/88
13 years old	122/77	126/81	133/89	121/77	124/81	132/89
14 years old	125/78	128/82	136/90	122/78	126/82	133/90
15 years old	127/79	131/83	138/91	123/79	127/83	134/91
16 years old	130/80	134/84	141/92	124/80	128/84	135/91

Systolic/diastolic blood pressures (mmHg, JCS2012)

The 90th, 95th, and 99th indicate 90th, 95th, and 99th percentiles, respectively.

<Pharmacokinetics>

Plasma concentrations of TAK-536 and its metabolites (M-I and M-II)

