7.4 Demographic and Other Baseline Characteristics

Analysis set:

Safety analysis set

Analysis variable(s):

Age (years) [6, 7, 8, 9, 10, 11, 12, 13, 14, 15]

Gender [Male, Female]

Height (cm) at Week 0 [Min \le - \le 99, 100 \le - \le 109, 110 \le - \le 119, 120 \le - \le 129, 130 \le - \le 139, 140 \le - \le 149, 150 \le - \le 159, 160 \le - \le 169, 170 \le - \le 179, 180 \le - \le Max]

Weight (kg) at Week 0 [Min \le - \le 19.9, 20.0 \le - \le 29.9, 30.0 \le - \le 39.9, 40.0 \le - \le 49.9, 50.0 \le - \le 59.9, 60.0 \le - \le 69.9, 70.0 \le - \le 79.9, 80.0 \le - \le Max]

 $[Min \le - \le 49.9, 50.0 \le - \le Max]$

BMI (kg/m²) at Week 0 [Min≤ - ≤14.9, 15.0≤ - ≤17.9, 18.0≤ - ≤20.9, 21.0≤ - ≤23.9, 24.0≤ - ≤26.9, 27.0≤ - ≤Max]

Disease duration (years) $[Min \le - \le 0.9, 1.0 \le - \le 1.9, 2.0 \le - \le 2.9, 3.0 \le - \le 3.9, 4.0 \le - \le Max]$

Type of hypertension [Essential hypertension, Secondary hypertension]

Drug induced hypertension [Yes, No]

Disease induced hypertension [Yes, No]

History of kidney transplantation [Yes, No]

Antihypertensive drugs prior to Run-in Period [Yes, No]

ACE inhibitors [Yes, No]

ARB [Yes, No]

DRI [Yes, No]

CCB [Yes, No]

Diuretics [Yes, No]

Alpha-blockers [Yes, No]

Beta-blockers [Yes, No]

Other [Yes, No]

RAS inhibitors (ACE inhibitors, ARB, and DRI) prior to Run-in Period [Yes, No]

Antihypertensive drugs at the start of Treatment Period I [Yes, No]

CCB [Yes, No]

Diuretics [Yes, No]

Alpha-blockers [Yes, No]
Beta-blockers [Yes, No]
Other [Yes, No]

Office sitting blood pressure (systolic) (mmHg) at Week 0 [Min \leq - \leq 109, 110 \leq - \leq 119, 120 \leq - \leq 129, 130 \leq - \leq 139, 140 \leq - \leq Max]

Office sitting blood pressure (diastolic) (mmHg) at Week 0 [Min \leq - \leq 69, 70 \leq - \leq 79, 80 \leq - \leq 89, 90 \leq - \leq 99, 100 \leq - \leq Max]

eGFR (mL/min/1.73 m²) [Min \le - \le 29, 30 \le - \le 59, 60 \le - \le 89, 90 \le - \le Max]

Analytical method(s):

The following analysis will be performed for the above analysis variables by weight group ($< 50 \text{ kg}, \ge 50 \text{ kg}$) and in the combined weight groups.

(1) Frequency distributions for categorical variables and summary statistics for continuous variables

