7.13 Changes in the Statistical Analysis Plan

Although home blood pressure is defined as a safety endpoint in the protocol, it will be also evaluated as an efficacy endpoint as described in 7.8.3 in this statistical analysis plan.

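### BMI is part of the primary safety endpoint, but the SAP specifies no BMI analysis after Week 0 and does not declare the omission

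*SAP*

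**What the plan says.** The protocol lists weight, height and BMI as the anthropometric part of the primary safety endpoint (5.2.1) and repeats the list at the head of the safety analysis (13.1.5). For continuous variables under that heading it commits to the following: "the observed values and the changes from the end of the Run-in Period (Week 0) will be summarized for each time point". It then adds: "In addition, individual figures of the observed values will be provided". Protocol 9.1.4 gives the BMI formula and its rounding.

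SAP 5.0 carries the same endpoint forward: "AEs, anthropometric (weight, height, and body mass index [BMI]) measurements, laboratory tests". SAP 7.11.3 is the section that analyses anthropometry after baseline. Its variable list has "Height, Weight" and its visit line is "Height and weight: Weeks 0, 12, 24, 40, and 52". Table 7.d sets visit windows for the same two measurements. The only SAP analysis that uses BMI is in 7.4, as "BMI (kg/m²) at Week 0".

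SAP 7.13, which records changes, contains one entry: "Although home blood pressure is defined as a safety endpoint in the protocol, it will be also evaluated as an efficacy endpoint". It says nothing about BMI.

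**The concern.** The SAP names BMI as a primary endpoint item in one section and leaves it out of the section that should analyse it. It therefore conflicts with the protocol and with itself, and nothing marks the difference as deliberate. Tables and figures are programmed from the SAP's variable lists, so following it as written gives no post-baseline BMI summary, change or figure at Week 24 or Week 52.

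The study follows children aged 6 to under 16 for 52 weeks, and protocol 8.1.3 itself expects their weight to change. Height and weight results do not replace BMI here. BMI combines the two measurements within each child, so the mean and SD of its change cannot be worked out from separate height and weight tables.

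**Working it through.** **Step 1. Trace each item of the endpoint sentence (protocol 5.2.1, SAP 5.0) to its post-baseline analysis in the SAP.**

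| Item | Post-baseline analysis in SAP |
|---|---|
| Adverse events | 7.11.1 |
| Weight | 7.11.3 |
| Height | 7.11.3 |
| BMI | none (Week 0 only, in 7.4) |
| Laboratory tests | 7.11.2 |
| Resting 12-lead ECG | 7.11.4 |
| Office standing blood pressure | 7.11.3 |
| Office sitting pulse rate | 7.11.3 |
| Office standing pulse rate | 7.11.3 |
| Home sitting blood pressure | 7.11.3 |

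That is 9 of 10 items covered. In the whole SAP, BMI appears only in the abbreviation list, in 5.0 and in 7.4. SAP 7.1.1 has no derivation for it.

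**Step 2. Count what is absent.** The schedule in protocol Appendix A is not available, so this assumes that BMI follows the height and weight visits. SAP 7.11.3 reports three groups: under 50 kg, 50 kg and over, and combined.

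- Week 52 analysis: post-baseline visits at Weeks 12, 24, 40 and 52. 4 visits × 3 groups = 12 observed-value summaries and 12 change summaries.
- Week 24 analysis: post-baseline visits at Weeks 12 and 24. 2 × 3 = 6 and 6. This also assumes that 7.11.3 is run at Week 24, since SAP 7.12 lists sections only for the Week 12 analysis.
- BMI case plots: absent from both.
- Week 12 interim: unaffected, because 7.11.3 is not among the sections listed in 7.12.

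**Step 3. Can BMI change be recovered from the height and weight tables?** A constructed example shows that it cannot. Two children both start at 140 cm and 40 kg, so BMI = 40 / 1.40² = 20.4.

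- Case A: one child gains 6 cm and 6 kg, giving 46 / 1.46² = 21.6, a change of +1.2. The other does not change (0.0). SD of change = 1.17 / √2 ≈ 0.8.
- Case B: one child gains 6 cm only, giving 40 / 1.46² = 18.8, a change of −1.6. The other gains 6 kg only, giving 46 / 1.40² = 23.5, a change of +3.1. SD of change = (3.06 + 1.64) / √2 ≈ 3.3.

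In both cases the height changes are 6 and 0 cm and the weight changes are 6 and 0 kg, so the means and SDs of height change and weight change are identical. The SD of BMI change is about 0.8 in one case and 3.3 in the other.

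**The case against.** The strongest reply is that the analysis is already prespecified. Protocol 13.1.5 names BMI and states what will be reported, protocol 13.1 gives the SAP the role of adding detail, and nothing in the SAP withdraws the commitment. BMI is also a fixed function of two variables that are collected, summarised and plotted, so it can be computed after lock by a formula already in the protocol. No threshold, test or decision uses it.

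Most of this is true, and it limits the importance of the point. It makes the defect an undeclared mismatch between SAP and protocol rather than the absence of any plan. It does not remove the mismatch: an explicit variable list without BMI produces no BMI output, and the case plots allow only partial reconstruction for individual children.

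The counts can also be challenged. The count of ten treats laboratory tests as one item; at a finer level, HbA1c (Table 9.a, diabetic patients only) is also missing from SAP 7.11.2.1. The count is correct for the items as the endpoint sentence names them. The protocol does not ask for a weight-group breakdown, so measured against the protocol alone the shortfall is 4 observed-value and 4 change summaries at Week 52, and 2 and 2 at Week 24. The Week 24 visits recur in the Week 52 analysis, so the two sets should not be added together.

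One practical point stands. SAP 7.1.3 selects the closest evaluable value for each test, and the Week 12 window in Table 7.d runs from Day 2 to Day 127. Without a rule, the height and weight used for one BMI value could come from different days.

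**Conclusion.** The concern holds. As written, the SAP gives no post-baseline analysis for BMI, a named part of the primary endpoint, and does not declare the departure from protocol 13.1.5. BMI is 1 of 10 named items, and 0 of 4 post-baseline visits have a BMI summary if it follows the height and weight schedule. With the other nine items covered and SAP 5.0 still listing BMI, an oversight is more likely than a decision, although the documents do not settle this.

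The correction should be made, but the consequence is small. BMI is descriptive, no error rate, power or sample-size figure changes, and the Week 12 interim is untouched.

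**What to change.** Add BMI to the variable list and visit line of SAP 7.11.3 at Weeks 0, 12, 24, 40 and 52, with observed values, change from Week 0 and case plots in the existing three groups. Put the derivation in 7.1.1, using the protocol 9.1.4 formula and rounding, and state that height and weight must come from the same measuring day. Extend Table 7.d to cover BMI.

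If BMI is meant to be reported only at baseline, say so in 7.13 with the reason.

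The cost is a few lines of SAP text plus the BMI tables and plots. BMI is computed from height and weight already collected, so no new data are needed.

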8.1.3 Dose and Regimen

During the Run-in Period, subjects will orally receive TAK-536 2.5 mg granules (placebo for the Run-in Period) if subjects weighing < 50 kg, or TAK-536 5 mg tablet (placebo for the Run-in Period) if subjects weighing ≥ 50 kg, once daily, before or after breakfast. During the Treatment Period, the same dose of the selected placebo during the Run-in Period will be the initial dose. After the initial dose, subjects will orally receive any of TAK-536 2.5 mg granules, TAK-536 5 mg, 10 mg, 20 mg tablet, once daily, before or after breakfast, if subjects weighing < 50 kg, or any of TAK-536 5 mg, 10 mg, 20 mg, 40 mg tablet, if subjects weighing ≥ 50 kg. For dose titration method, see Section 6.1 Study Design.

Because weight is likely to change during the study, the highest dose for the subjects is allowed to be changed if dose adjustment by changing of weight is required during the Treatment Period II.

The investigator or subinvestigator may select the timing of the study drug administration (i.e., before or after breakfast) in consideration of subject lifestyle but should not change this timing throughout the study. The investigator or its designee will record the guidance provided about the timing of the study drug administration (before or after breakfast) at the start of the Run-in Period (Week -2) in the eCRF.

At the start of the Run-in Period (Week -2), the study drug for the Run-in Period will be administered on the same day after completing all tests, observations, and evaluations. In case that

subjects take RAS inhibitors in the morning of the visit day, the administration of the study drug for the Run-in Period will be started from the next day.

Except for Week 16, subjects will visit the study site on each visit day without taking the study drugs, and receive them only after completing all tests, observations, and evaluations.

On the visit of Week 16, subjects, the subjects' parent or the subjects' legal guardian will be instructed to visit the study site after taking the study drug and the tests, observations, and evaluations 2 hour (acceptable time window, 1 to 3 hours) after taking the study drug will be performed.

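### Height and weight are primary safety endpoints in growing children but are summarised only on the raw scale, with no age- and sex-standardised score or growth reference

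*SAP*

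**What the plan says.** Protocol 5.2.1 opens its list of primary endpoints with "AEs, anthropometric (weight, height, and body mass index [BMI]) measurements, laboratory tests", and SAP 5.0 repeats the anthropometric item.

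Protocol 13.1.5 sets the analysis: "For continuous variables, the observed values and the changes from the end of the Run-in Period (Week 0) will be summarized for each time point". It then adds: "In addition, individual figures of the observed values will be provided".

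SAP 7.11.3 carries this out for height and weight. The visits are "Height and weight: Weeks 0, 12, 24, 40, and 52". The outputs are "Summary statistics for observed values and changes" plus case plots, by weight group (cut at 50 kg) "and in the combined weight groups". Summary statistics, as defined in SAP 7.1.1, do not include a confidence interval. Age and sex are not strata for these variables. SAP 7.4 tabulates both at baseline, and SAP 7.8.4.7 uses sex as a stratum for blood pressure only.

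There is one arm (SAP 7.8.4.3). Protocol 8.1.3, on dosing, notes in passing that weight will not stay constant: "Because weight is likely to change during the study".

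Other variables do have a yardstick. Target blood pressure is judged against the age and sex values of Table 5.a. Home blood pressure is judged against the 99th percentile plus a margin (SAP 9.3). Laboratory values are judged against normal ranges and, for selected items, markedly-abnormal criteria (SAP 7.11.2.1 and 9.2). Height and weight have none.

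**The concern.** A change from baseline can be read when its expected value without a drug effect is known. For most safety variables here that value is roughly zero. For height and weight in children over a year it is a positive amount that varies with age and sex. The plan does not state it, and there is no control arm to supply it.

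The mean change in cm or kg is therefore governed largely by who was enrolled. A modest slowing of growth in a young cohort could give the same mean as ordinary growth in an older one. Excess weight gain could be masked in the same way. The 50 kg cut is a dosing boundary and only a crude proxy for age, because ages and both sexes remain mixed on each side of it.

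Two SAP rules add to the difficulty:
- Table 7.d accepts a height from Study Day 2 to 127 as Week 12 and from Day 128 to 225 as Week 24. Children summarised under one visit may have had quite different times in which to grow.
- Missing values are simply excluded (SAP 7.8.4.2), so the age mix can shift from visit to visit.

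What is at stake is whether a primary safety table can be interpreted. No planned test is biased.

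**Working it through.** **The plan's own figure.** The plan gives no figure for growth. Its only power statement concerns blood pressure with 50 subjects (SAP 6.0). For a one-sample t-test with df 49, the noncentrality is |mean|/SD × √50:
- diastolic: 6.5/10.5 × 7.07 = 4.38, power 99.0%
- systolic: 9.5/15.5 × 7.07 = 4.33, power 98.9%

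The stated floor of 90% holds, but it says nothing about height or weight.

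**How far the age mix moves a normal mean.** All growth values here are assumptions; none is in the documents. Suppose younger children gain *hi* cm a year and the oldest gain *lo* cm a year, with a share *f* of the oldest. Expected pooled gain = (1 − f) × hi + f × lo.

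| Assumed hi / lo (cm/year) | f = 0.2 | f = 0.8 | Swing |
|---|---|---|---|
| 5 / 2 | 4.4 | 2.6 | 1.8 |
| 6 / 1 | 5.0 | 2.0 | 3.0 |
| 7 / 0.5 | 5.7 | 1.8 | 3.9 |

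**Sampling precision of the raw mean.** Half-width = t(0.975, 49) × SD/√50, with t = 2.01.
- SD of gain 1.5 cm (assumed): 2.01 × 1.5/7.07 = 0.43 cm
- SD of gain 3 cm (assumed): 2.01 × 3/7.07 = 0.85 cm

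The swing is between 1.8/0.85 ≈ 2 and 3.9/0.43 ≈ 9 times the half-width. Under these assumptions, what an observed mean signifies depends more on the age mix than on sampling error.

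**A worked reading.** Take an observed mean gain of 4.5 cm where the enrolled mix should have gained 5.5 cm (both assumed). The 95% CI is 4.07 to 4.93 cm for an SD of 1.5, or 3.65 to 5.35 cm for an SD of 3. Either interval lies wholly inside the 1.8 to 5.7 cm range of normal means, so the raw table alone raises no flag. Either interval also excludes 5.5 cm, so the shortfall would show once the expectation for the actual mix was worked out. The plan does not include that step.

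**Precision on a standardised scale.** For an assumed SD of one-year change in height SD score of 0.2 to 0.5, the half-width is 2.01 × 0.2/7.07 = 0.06 to 2.01 × 0.5/7.07 = 0.14. The change detectable with 90% power is 0.09 to 0.23. Fifty subjects are enough for a useful interval.

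**Whole-centimetre recording** (Protocol 9.1.4). Rounding two heights adds an SD of √(2/12) = 0.41 cm to each child's change. At Week 12 the assumed gain at 5 to 7 cm a year is only 12/52 of that, 1.2 to 1.6 cm, so individual early changes are coarse. The rounding contribution to the mean of 50 is 0.41/7.07 = 0.06 cm.

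No corresponding calculation was made for weight. The argument there is the same in kind.

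**The case against.** The strongest reply has four parts.

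1. **The plan offers more than a pooled mean change.** Observed values, case plots and results by weight group are all planned, and a child whose height flattens could be seen in an individual plot. This stands. A reader might infer that only a pooled raw change is produced; the documents do not support that. The plots, however, have no specified reference curve or criterion.

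2. **The age and sex mix will be known.** SAP 7.4 tabulates age by single year, and sex, by weight group and overall. A reader might infer that normal and impaired growth cannot be told apart in this study. That goes too far: date of birth and sex are collected (Protocol 9.1.2), and the worked reading shows a shortfall emerging once the expectation is computed. The limitation belongs to the planned outputs, which leave that computation to the reader.

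3. **A standardised score may not have an expected change of zero here.** Protocol 6.2 expects many children with renal dysfunction, 7.1 admits kidney-transplant recipients, and 7.3.2 permits systemic steroids. A reader might take any non-zero change as a drug effect. Without a control arm that inference fails, and an age- and sex-based score does not adjust for pubertal timing either. This stands, and limits what the fix can claim.

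4. **No growth hypothesis is stated.** Protocol 6.2 justifies the primary endpoints only as customary safety variables, and 10.2.1.3 names hypotension and renal dysfunction as the special concerns. Physical examination and adverse event reporting could also pick up evident growth problems. This is fair and bears on severity. Even so, a descriptive primary endpoint needs a reference value to be readable.

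**Conclusion.** The point holds in a limited form. Height and weight are summarised only on the raw scale, and the raw mean change has no interpretable null value. It depends largely on the enrolled age and sex mix, so the planned summaries do not show whether growth departs from expectation.

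The SAP and protocol do not contradict each other on these two variables, and no planned estimate or test is biased. This is an inexpensive improvement to a primary safety display.

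The size rests wholly on assumed growth values: a normal pooled height gain anywhere from about 1.8 to 5.7 cm a year, against a half-width of 0.43 to 0.85 cm. The qualitative conclusion needs only that expected growth differs by age and sex and that no reference is planned.

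**What to change.** - **SAP 7.1.1:** derive age- and sex-specific SD scores for height and weight at each visit from a named, prespecified Japanese growth reference. Use age at measurement. The target-blood-pressure rule in the same section fixes age at consent; applied to growth over a year, that would let ordinary growth appear as a rise in the score.
- **SAP 7.11.3:** summarise the SD score and its change from Week 0, with 95% CI, at Weeks 12, 24, 40 and 52, beside the raw values and case plots.
- **Interpretation:** state that a non-zero change shows departure from reference growth but cannot by itself separate drug effect from renal disease, transplantation, permitted steroids or pubertal timing.

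**Cost:** SAP wording and one derivation from data already collected. A reference has to be chosen, and fixing it in advance avoids a choice made after seeing the data. Whole-centimetre heights limit precision at the early visits.
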